#### 2) Analysis of CDRS-R total score subscales and item 13 (suicidal ideation), and CGI-S score

All usable data obtained at stipulated time-points after study drug administration will be used, and a linear model (MMRM) will be applied, with change from baseline taken to be a response variable; treatment group, observation time-points, and interaction between treatment group and observation time-points taken to be fixed effects; baseline value, and age (<12, ≥12) taken to be covariates, and the covariance structure for error variance taken to be unstructured. In this step, the degree of freedom will be adjusted using the approximation of Kenward and Roger. On the basis of this model, the estimated difference between the duloxetine and placebo groups at each time-point after administration initiation, and the 95% confidence interval, and the p-value, will be calculated.

#### 3) CGI-S score category distribution

The CGI-S score category distribution will be summarized for each group at baseline and at the final evaluation (week 6 of administration or discontinuation of the treatment period).

## 10. Safety evaluation

Safety analyses will be performed with the safety-analysis set.

### 10.1 Adverse events and adverse drug reactions

Adverse events occurring at or after the initial administration of the study drug will be evaluated. Reported adverse events will be converted to Medical Dictionary for Regulatory Activities (MedDRA) terms, and tabulated by system organ class and preferred term.

- 1) For each treatment group, the number of subjects with a given adverse event and the number of cases will be determined, and the incidence rate and 95% confidence interval will be calculated. The incidence rate will be obtained as the proportion of subjects in the analysis set with a specific adverse event, and the confidence interval for the incidence rate will be determined by the Clopper-Pearson method. In addition, the incidence rates will be compared between treatment groups using Fisher's exact test. Totaling will be performed in a similar manner to above with deaths, other serious adverse events, adverse events leading to administration discontinuation, adverse events leading to dose reduction, adverse drug reactions, deaths as adverse drug reactions, other serious adverse drug reactions, adverse drug reactions leading to administration discontinuation, and adverse drug reactions leading to dose reduction. The relevant definitions are shown below.

Death	Adverse event with "Death" as the outcome
Other serious adverse event	Adverse event in the seriousness category "Serious", except for death
Adverse event leading to administration discontinuation	Adverse event for which the study drug action is "Administration discontinuation"
Adverse event leading to dose reduction	Adverse event for which the study drug action is "Dose reduction"
Adverse drug reaction	Adverse event with the causal relationship with the study drug judged to be other than "Not related"
Death as adverse drug reaction	Death, with the causal relationship with the study drug judged to be other than "Not related"
Other serious adverse drug reaction	Other serious adverse event with the causal relationship with the study drug judged to be other than "Not related"
Adverse drug reaction leading to administration discontinuation	Adverse event leading to administration discontinuation, with the causal relationship with the study drug judged to be other than "Not related"
Adverse drug reaction leading to dose reduction	Adverse event leading to dose reduction, with the causal relationship with the study drug judged to be other than "Not related"

- 2) For each treatment group, the number of subjects with a given adverse event, the number of cases, and the incidence rate will be determined by adverse event system organ class and preferred term. However, when calculating the number of subjects with a given adverse event and the incidence rate, if the same adverse event occurs more than once with the same subject, these events will be taken to be have affected one subject. Adverse drug reactions will be tabulated similarly.
- 3) With respect to adverse events with an incidence of 2% or more in at least one treatment group, the number of subjects, number of cases, and incidence rate will be calculated for each adverse event preferred term. Adverse drug reactions will be tabulated similarly.
- 4) For each treatment group, the number of subjects and incidence rate will be calculated for each severity and outcome category, by adverse event system organ class and preferred term. If the same adverse event occurs more than once in different categories with the same subject, it will be taken to have occurred once, in the category with the highest of the below priority ranks. Adverse drug reactions will be tabulated similarly.

Priority rank	Survey item category	
	Severity	Outcome
1	Severe	Death
2	Moderate	Recovery with sequelae
3	Mild	No improvement
4		Partial recovery
5		Recovery
6		Unknown

- 5) For each treatment group, the number of subjects and the incidence will be calculated for each onset timing category (weeks 0 to 1; weeks 1 to 2; weeks 2 to 3; weeks 3 to 6; later than week 6) for adverse events during the treatment period, by system organ class and preferred term. The denominator of the incidence rate will be the number of subjects with administration duration no shorter than the lower limit of each onset time category. The onset timing will be calculated as follows:  

$$\text{Onset timing [day]} = (\text{onset date}) - (\text{administration initiation date}) + 1$$
When calculating the number of subjects and the incidence rate, if the same adverse event occurs in different categories more than once in the same subject, it will be taken to have occurred with one subject in each of the relevant categories. Adverse drug reactions will be tabulated similarly.
- 6) With subjects in the safety analysis set who are transferred to the tapering period, adverse events that occur during the tapering period will be summarized. For each treatment group, the number of subjects with a given adverse event, the number of cases, and the incidence rate will be determined by adverse event system organ class and preferred term. However, when calculating the number of subjects with a given adverse event and the incidence rate, if the same adverse event occurs more than once with the same subject, this event will be taken to be have affected one subject. Adverse drug reactions will be tabulated similarly.

- 7) For each treatment group, with respect to adverse events for which the below standard MedDRA queries (SMQ) are applicable, the number of subjects, number of cases, and incidence rate will be determined by system organ class and preferred term. However, when calculating the number of subjects with a given adverse event, and the incidence rate, if the same adverse event occurs more than once with the same subject, this event will be taken to be have affected one subject.

SMQ	Range
Suicide/self-injury	Broad search
Hostility/aggression	Broad search

- 8) With respect to the duloxetine group, the number of subjects and incidence rate will be calculated for each duloxetine dose category (20 mg, 40 mg, 60 mg) at the adverse event onset date, by system organ class and preferred term. When calculating the number of subjects and the incidence rate, if the same adverse event occurs in different categories more than once in the same subject, it will be taken to have occurred with one subject in each of the relevant categories. Adverse drug reactions will be tabulated similarly.
- 9) Subgroup analyses will be performed for the below demographic factors. For each treatment group, the number of subjects and the incidence rate will be calculated by adverse event system organ class and preferred term.
- Age (<12, ≥12)
  - Sex (male, female)

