3.1 Study design

[figure not shown]
This study is to be a multicenter, randomized, placebo-controlled, double-blind, parallel-group, comparative study with children and adolescent patients with depressive disorder, with the target number of subjects being 148. It will consist of the following four periods: Screening period (1-3 weeks), treatment period (6 weeks), Tapering period (1 week), Follow-up period (1 week), (total: up to 11 weeks). During the treatment and tapering periods (total: 7 weeks), duloxetine or placebo will be administered orally, once daily after breakfast. Subjects who transfer to the extended long-term treatment study [study no.: 1702A3632 (NCT03395353)] will transfer to the extended study after completion of the tapering period.

- Screening period: After obtaining informed consent, eligibility has to be confirmed at Visit 1, and subjects for whom this is confirmed will then be pre-registered. In addition, the first session of psycho-education will be provided, and the subjects' conditions will be assessed.
- Treatment period: Eligibility will be confirmed again at Visit 2, and subjects for whom this is confirmed will then be registered. The subjects will then be allocated randomly, with double-blinding, to the duloxetine and placebo groups, in a 1:1 ratio, and will be orally administered duloxetine or placebo once daily after breakfast, for 6 weeks. With the duloxetine group, administration will be initiated at 20 mg/day, and increased to 40 mg/day at Visit 3, 1 week later. From Visit 4, 1 week after Visit 3, if the CGI-S score is 3 or higher, and there are no concerns about safety, the dose will be increased to 60 mg/day. In addition, from Visit 5, after the dose has been temporarily increased to 60 mg/day, if there are safety-related problems, it can be reduced again to 40 mg/day. If the CGI-S score is ≥ 3 , and there are no safety-related problems, after confirming the subject's clinical condition and safety, the dose can be increased again. When the dose is to be increased from 20 to 40 mg/day, or from 40 to 60 mg/day for the first time, the pre-increase dose must be administered for at least 7 days. Visit 6 is a visit that can be made to the hospital in connection with dose increase, decrease, etc.

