4.5 Withdrawal from study or discontinuation of administration

The principal investigator or sub-investigator will as far as possible encourage subjects to complete the study, but subjects can withdraw for any reason. The principal investigator or sub-investigator will notify the sponsor about all discontinuations. If one or more of the following is applicable, the principal investigator or sub-investigator will discontinue study drug administration to the subject, and then discontinue the study. Completion of the study means completion of administration and observation up to Visit 9, or up to Visit 10 in the case of subjects who do not transfer to the extended long-term treatment study [study no.: 1702A3632 (NCT03395353)].

- The principal investigator or sub-investigator judges discontinuation to be necessary due to one or more serious or intolerable adverse events.
- The principal investigator or sub-investigator judges that insufficient efficacy of the study drug has resulted in aggravation of the primary disease, making discontinuation necessary.
- Pregnancy of the subject.
- The subject or his/her legal representative expresses the wish to withdraw from the study.
- The ineligibility of the subject is revealed during the screening period.
- The ineligibility of the subject is revealed after initiation of study drug administration.
- Administration of duloxetine at a dose of 40 mg/day or higher is difficult at or after Visit 3.
- Change in hospitalization status is necessary between Visits 1 and 8.
- The subject is unable to visit hospital due to moving home, transferring to a different hospital, etc.
- Death of the subject.

- It is judged that management of abnormal hepatic function test results is necessary, as is withdrawal on the basis of the discontinuation criteria (Appendix 2).
- Discontinuation is judged by the principal investigator or sub-investigator to be necessary for any other reason.

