6.2 Treatment during study treatment period (concomitant drugs/therapies)

Treatment after Visit 1 is taken to be concomitant treatment (concomitant drugs/therapies).

The investigator or sub-investigator will record in the CRF the following information about treatments (ethical drugs, over-the-counter drugs, and non-pharmaceutical therapies) administered to the relevant subject during the treatment period, that is, between Visit 1 and Visit 10 (completion of the follow-up period), or Visit 9 (completion of the tapering period) if the subject is transferred to the extended long-term treatment study [study no.: 1702A3632 (NCT03395353)]:

- Name of the concomitant drug or non-pharmaceutical therapy
- Administration route
- Occurrence or non-occurrence of dosage changes, and whether use is as-needed basis or not
- Treatment period
- Reasons for use

However, the following drugs do not have to be recorded in the CRF unless they are the cause of adverse events:

- Drugs for diluting solutions, such as physiological saline solution
- Drugs used in medical procedures, etc., with the drug itself not being for treatment, such as alcohol disinfection, and heparin lock.
- Items that are not recognized as drugs, such as foods. However, health foods, etc., with ingredient of contraindicated drugs or restricted drugs have to be recorded in the CRF.
- Fluid replacement or infusion solution, unless used to treat adverse events.
- Drugs used for tests, such as contrast agents and pre- and post-medication

6.2.1 Prohibited drugs and therapies:

Use of the below drugs, or over-the-counter drugs with equivalent effects, is prohibited from Visit 1 through Visit 9. (completion of the tapering period):

The first group of contraindicated drugs may affect therapeutic evaluation:

- 1) Antidepressants
- 2) Anxiolytics
- 3) Soporific agents, other than the “Permitted soporific agents” in Section 6.2.2 .
- 4) Antipsychotics

- 5) Antiparkinsonian agents
- 6) Anticonvulsants
- 7) Mood-stabilizers (lithium carbonate, carbamazepine, sodium valproate)
- 8) Psychostimulants
- 9) Adrenal corticosteroids (excluding topical agents, such as ear drops, nose drops, eye drops, topical skin formulations, and inhaled formulations).
- 10) Interferon formulations
- 11) Any of the following drugs, which might affect the metabolic/agonistic activities of serotonin or noradrenaline:
 - Cyproheptadine hydrochloride (Periactin[®], etc.)
 - Dimetotiazine mesilate (Migristene[®])

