7.6.7.2 Assessment period

Adverse events occurring between obtaining the legal representative's informed consent and 7 days after the final administration of study drug (the follow-up period) will be assessed. Adverse events that occur before initiation of administration in the extended long-term treatment study (study no.: 1702A3632), in subjects transferred to that study, will also be assessed. In the case of withdrawn subjects, the principal investigator or sub-investigator will assess adverse events up to 7 days after final administration of the study drug. Appropriate follow-up will be continued until one of the following, and the outcome will be determined on that basis: (i) the relevant adverse event recovers to the pre-administration state; (ii) the subject's condition stabilizes or becomes chronic; (iii) the subject is lost to follow-up; or (iv) the principal investigator or sub-investigator judges further assessment to be unnecessary. If the relevant subject transfers to the extended long-term treatment study (study no.: 1702A3632), follow-up of the adverse event will be continued after initiation of administration in that study, and it will be recorded in the CRF that the relevant adverse event continued after initiation of administration in the extended long-term treatment study. In addition, if the subject stops visiting hospital during the study, he/she will be followed up by an appropriate method such as by telephone, and the findings will be entered in the CRF.

If the above adverse event follow-up has to be continued for 28 days or more after completion of administration, the outcome at the earliest date after 28 days after completion of administration will be recorded in the CRF.

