7.6.7.11 Adverse events during study drug administration

Adverse events with onset after the initial study drug administration are taken to be treatment-emergent adverse events.

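### The by-arm adverse-event comparison in SAP 10.1 has no analysis cut-off common to children who do and do not transfer to the extension study

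*SAP*

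**What the plan says.** **Start of counting.** SAP 10.1 opens with "Adverse events occurring at or after the initial administration of the study drug will be evaluated". Protocol 7.6.7.11 defines treatment emergence in the same way: "Adverse events with onset after the initial study drug administration are taken to be treatment-emergent adverse events". Neither sentence gives an end.

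**Measure and test.** SAP 10.1 item 1 takes incidence as a simple proportion of the analysis set, with a Clopper-Pearson interval, and compares arms by Fisher's exact test. There is no person-time and no common closing day.

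**End of collection.** Protocol 7.6.7.2 supplies this. In general, events up to "7 days after the final administration of study drug (the follow-up period) will be assessed". For children who transfer, "Adverse events that occur before initiation of administration in the extended long-term treatment study" are also covered. The section does not say how the 7-day rule works once extension dosing has begun.

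**Who has the follow-up week.** Protocol 3.1 makes this week drug-free and says transferring children "will transfer to the extended study after completion of the tapering period". Protocol 4.5 defines completion as Visit 9, "or up to Visit 10 in the case of subjects who do not transfer to the extended long-term treatment study". The concomitant-treatment record in protocol 6.2 splits the same way: Visit 10, "or Visit 9 (completion of the tapering period) if the subject is transferred to the extended long-term treatment study".

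**Tables limited to a period.** SAP 10.1 item 5 tabulates treatment-period events by onset time, and item 6 tabulates taper events among children who enter the taper. Neither is stated to carry the Fisher test, and no table isolates the follow-up week.

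**The concern.** Whether a child is observed for the last week depends on transfer, which is decided after randomisation. A crude proportion takes no account of that. If more children transfer in one arm, that arm has fewer observed days, and some of the difference in incidence comes from how long children were watched and not from the drug.

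The week in question also matters clinically. Protocol 3.1 includes the taper to limit events caused by stopping drug, and the week after it is a natural place for such events to appear. The suicide/self-injury query in SAP 10.1 item 7 has the same unaligned window, and protocol 7.6.7.6 treats suicide-related events as of special concern.

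Other safety measures in the SAP do have a common end. The final evaluation for vital signs and laboratory tests is week 7 or discontinuation (SAP 6.3, 10.2, 10.3), and the C-SSRS runs to week 7 or discontinuation (SAP 10.5). Adverse events are the exception.

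**Working it through.** The plan states no figure for adverse-event incidence, observation time or transfer, so there is none of its own to reproduce on this point. The number per arm comes from protocol 8.2: 66 / 0.9 = 73.3, rounded up to 74 per arm, 148 in total.

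**Step 1: nominal observation** (protocol 3.1 and 7.8)

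- Extension started directly after taper: 42 + 7 = 49 days.
- No transfer: 42 + 7 + 7 = 56 days.
- Gap: 7 days, or 7/56 = 12.5% of the longer window.

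A transferring child with a drug-free gap before the first extension dose is observed during that gap, so 7 days is the most that is lost. The documents do not give the length of the gap.

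**Step 2: artefact when the drug has no effect**

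Let P be the incidence to the end of taper, q the risk of a first event in the follow-up week among children without one so far, and t1 and t2 the transfer proportions. Observed incidence in arm i is P + (1 − P) × q × (1 − ti). The spurious difference between arms is

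(1 − P) × q × |t1 − t2|.

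P, q, t1 and t2 are all assumptions. P = 0 stands for an event term seen only after stopping drug.

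| Transfer by arm | P = 60% | P = 30% | P = 0 |
|---|---|---|---|
| 80% v 80% | 0 | 0 | 0 |
| 80% v 60%, q = 5–15% | 0.4–1.2 points | 0.7–2.1 points | 1–3 points |
| 90% v 50%, q = 5–15% | 0.8–2.4 points | 1.4–4.2 points | 2–6 points |

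Worked cell: P = 30%, q = 15%, 80% v 60% gives 0.70 × 0.15 × 0.20 = 0.021, or 2.1 points. The arm with more transfer looks safer.

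**Step 3: effect on the Fisher test** (exact enumeration, 74 per arm, two-sided 0.05, no drug effect)

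- Common events (P = 30% or 60%), transfer differing by arm as above: rejection 3.3–5.8%. With equal transfer it is 3.2–3.5%.
- Follow-up-only term, q = 15%: 0.6% with equal transfer, 5.3% at 80% v 60%, 24% at 90% v 50%.
- Follow-up-only term, q = 5%: below 1% in all three cases.

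**Step 4: dilution when transfer is equal**

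Suppose a true follow-up-week risk of 15% v 5%, for a term seen only then. With transfer t in both arms and the whole arm as denominator, the observed difference is 10 × (1 − t) points:

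| t | Observed difference | Fisher rejection |
|---|---|---|
| 0 | 10 points | 44% |
| 50% | 5 points | 15% |
| 80% | 2 points | 1.2% |
| 90% | 1 point | 0.1% |

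**Step 5: with a cut-off at the end of taper**, every child who completes the taper has a nominal 49 days whether or not the child transfers. The transfer-driven part of the difference is then zero.

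**The case against.** Four arguments tell against a stronger reading.

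- **The window is not open-ended.** A reader of SAP 10.1 alone might infer that it is. Protocol 7.6.7.2 and footnote f of the study schedule (protocol Appendix 1, repeated in SAP Appendix 1) end collection for each child. What is missing is a common analysis cut-off. This stands.
- **Extension-phase events are not shown to be counted here.** One might read the 7-day rule as crediting events under extension treatment to the randomised arm. Protocol 7.6.7.2 treats the first extension dose as the boundary, and asks only for a note that an ongoing event continued past it. Nothing says that new events under extension dosing enter this study's data. The text is unclear on the point, but does not support that reading.
- **Bias is not demonstrated.** Transfer alone biases nothing. The documents give neither transfer rates nor transfer criteria, so a link with response or tolerability is plausible but unsupported. For common events the Fisher test stays near its nominal level. The 24% figure needs 90% v 50% transfer, a 15% risk and a term seen only after stopping.
- **Items 5 and 6 already give by-arm tables that do not depend on the follow-up week.** This stands as partial mitigation. They do not carry the Fisher comparison, and they do not separate out the follow-up week.

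Early withdrawal can also shorten observation, and by more than 7 days. A cut-off that ignores transfer does not remove that. It does mean that the rule must say what happens to children who stop without a taper (protocol 5.2).

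**Conclusion.** The gap is real and minor. SAP 10.1 compares crude proportions over a period that is nominally 49 or 56 days, depending on an event after randomisation. The resulting artefact is zero if transfer is equal between arms and unrelated to event risk. Under assumed 80% v 60% transfer and 5–15% risk in the follow-up week, it is about 0.4–2 points for common events and 1–3 points for events seen only after stopping drug. Direction and true size cannot be known from the documents.

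The documents do not support a conclusion that the overall incidence or its Fisher test is materially biased. Two narrower results hold: rare, discontinuation-type terms are the most exposed, and even equal transfer shrinks a genuine follow-up-week difference when all children stay in the denominator. This is a cheap improvement to the analysis, not a flaw that threatens the trial's conclusions.

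**What to change.** Add a cut-off to SAP 10.1 that does not depend on transfer. Apply it to the by-arm incidence and Fisher tests of item 1 and to the tables of items 2–4, 7 (including the suicide/self-injury query) and 9.

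- Count events with onset from first dose through the end of the taper week (Visit 9 or taper discontinuation).
- For children with no taper, count through 7 days after the last treatment-period dose.
- In every case, count only events before any extension dose.
- Show later events in a separate table, with children still under observation and not transferred as the denominator.
- Report the proportion transferring, by arm.
- Keep the all-events table.

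Protocol 7.6.7.1 already has the date and time of onset recorded for each event, so no new adverse-event data are needed. The first extension-dose date must be available to the programmers; the documents do not say which database holds it. The cost is SAP wording and one repeated set of tables. The downside is that follow-up-week events leave the compared table, which is why the separate table and the all-events table are both needed. The sample size does not change.
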